2 PROTOCOL SYNOPSIS

Title: A Phase II, Open-Label Safety and Efficacy Study of an Autologous Neo-Kidney Augment (NKA) in Patients With Type 2 Diabetes and Chronic Kidney Disease (RMCL-CL001)

Therapeutic Product: NKA is made from expanded autologous selected renal cell population (SRC) obtained from the patient's kidney biopsy. To manufacture NKA, kidney biopsy tissue from each enrolled patient will be sent to Twin City Bio, LLC, Winston Salem, North Carolina, where renal cells will be expanded and SRC selected. SRC will be formulated in a gelatin based hydrogel at a concentration of 100 x 10^6 cells/mL, packaged in a 10 mL syringe, and shipped to the clinical site for use.

Study Objectives:

Primary Objective: The primary objective of the study is to assess the safety and efficacy of NKA injected in one recipient kidney and determine if two injections of NKA provide stabilization of renal function.

- Primary Safety Outcome Measures: procedure and/or product related adverse events (AE's) through 12 months following the initial NKA injection.
- Primary Efficacy Outcome Measures: serial measurement of serum creatinine and estimation of GFR through 6 months following the second cell injection

Secondary Objective: The secondary objective of the study is to assess the safety and tolerability of NKA administration by assessing renal-specific adverse events over a 12 month period following a patient's first NKA injection.

• Secondary Safety and Tolerability Outcome Measures: renal-specific laboratory assessments through 12 months following the last NKA injection under this protocol, whether first or second.

Exploratory Objective: Exploratory objectives of the study are designed to assess the impact of NKA on renal function over a 12 month period following the initial NKA injection.

- Exploratory Outcome Measures: clinical diagnostic and laboratory assessments of renal structure and function (including eGFR, serum creatinine, and proteinuria) to assess changes in the rate of progression of renal disease; and effect of method of injection on these parameters.
- Exploratory quality of life outcome measure will be the Kidney Disease Quality of Life survey obtained at baseline and at 1, 3, 6, 7, 9, 12, 15, 18, 30, and 42 months after a patient's first NKA injection.

Study Design: Multi-center, prospective, open-label, single-group study. All enrolled subjects will be treated with up to two injections of NKA at least 6 months apart.

Randomization: Open-label, non-randomized.

Control Group: Each subject will serve as his or her own control; the patient's previous medical history, which must include a minimum 6 month period of observation of renal function, will serve as the comparator for rate of progression of renal insufficiency.

Sample Size: Up to 30 subjects will be injected with NKA. As this is a Phase II safety and efficacy study, robust statistical analysis will not be performed. Therefore, the sample size proposed for this study is a size typical for the active treatment group in Phase II studies, allowing for identification of safety outcomes and early efficacy in a limited population.

Study Population:

Male or female patients 30 to 70 years of age with Type 2 diabetes mellitus and CKD with eGFR between 20 and 50 mL/min/1.73m². An enrolled patient should have sufficient historical clinical data to determine his or her individual rate of CKD disease progression.

Inclusion Criteria: Unless otherwise noted, inclusion criteria must be met at Screening and prior to injection.

- 1. Male and female subjects, age 30 to 70 years on the date of informed consent.
- 2. Patients with type 2 diabetes mellitus (T2DM).
- 3. Patients with a well-established diagnosis of diabetic nephropathy as the underlying cause of their renal disease.
- At screening, patients not previously injected with NKA with CKD defined as a GFR of 20 50 mL/min/1.73m² inclusive. Patients previously treated with a single NKA injection with eGFR 15 to 60 mL/min may also enroll in this clinical trial.
- Microalbuminuria that cannot be explained by an alternative diagnosis. Microalbuminuria is defined as urinary albumin-creatinine ratio (UACR) ≥ 30 mg/g or urine albumin excretion ≥ 30 mg/day on 24 hour urine collection.
- 6. Prior to biopsy, systolic blood pressure between 105 and 140 mmHg (inclusive) and diastolic blood pressure ≤90 mmHg.
- 7. Ongoing and stable treatment with ACEI or ARB initiated at least 8 weeks prior to enrollment. Treatment must be stable for the 6 weeks immediately prior to injection. Stable treatment is defined as dose adjustment to no less than ½ of the current dosage and no more than 2X the current dosage over the 6 week period immediately prior to injection; dose interruptions of up to 7 days due to medical necessity are allowed. Patients who are intolerant to ACEI or ARBs may be included as long as they have stable BP within the acceptable limits.
- 8. Minimum of 2 measurements of eGFR or sCr taken at least 3 months apart (prior to screening) and within the previous 12 months to define the rate of progression of CKD. The patient should have sufficient historical data to provide a reasonable estimate of the rate of progression of CKD as determined following consultation with the Medical Monitor (to insure sufficient data is available). In addition, the rate of progression of CKD must be consistent over time. There is no defined rate of progression that is required to qualify for inclusion.
- 9. Willing and able to refrain from use of NSAIDs (including aspirin) and clopidogrel, prasugrel, or other platelet inhibitors peri-procedure (i.e., before and after both the biopsy and injection). The wash-out period before and after each procedure should be 7 days. Willing and able to refrain from use of fish oil and dipryridamole for 7 days before and 7 days after each procedure.
- 10. Willing and able to cooperate with all aspects of the study.
- 11. Willing and able to give signed informed consent.

Exclusion Criteria: Patients may not be enrolled if they meet any of the exclusion criteria listed below. Criteria should be assessed at Screening and before injection unless noted otherwise.

- 1. Type 1 diabetes mellitus (DM).
- 2. History of a renal transplant.
- 3. HbA1c > 10% at Screening. Patients with HbA1c > 8% at the time of screening should be offered diabetic teaching and advised to consult their primary physicians for further diabetic management.
- 4. Hemoglobin levels < 9 g/dL prior to injection. Hemoglobin levels should be measured within 48 hours before the procedure or per site standard practice.
- 5. Known allergy to kanamycin or structurally similar aminoglycoside antibiotics (as kanamycin is used during manufacture of NKA).
- 6. Abnormal coagulation status as measured by APTT, INR, and/or platelet count at Screening.
- 7. Not a good candidate for the injection procedure (based on the assessment of the surgeon who will be performing the injection) including patients who are morbidly obese, have excessive fat surrounding the kidney, have BMI > 45, or who are otherwise at excessive risk for serious complications.
- 8. Clinically significant infection requiring parenteral antibiotics within 6 weeks of injection.
- 9. Patients with small kidneys (average size < 9 cm) or only one kidney, as assessed by MRI or renal US at screening or if previously done within 1 year of screening.
- 10. Patients with a rapid decline in renal function over the last 3 months prior to injection or acute kidney injury.
- 11. Patients with any of the following conditions prior to injection: renal tumors, polycystic kidney disease, renal cysts or other anatomic abnormalities that would interfere with injection procedure (e.g., cysts in the pathway of the injection), hydronephrosis, skin infection over proposed injection sites, or evidence of a urinary tract infection.
- 12. Female subjects who are pregnant, lactating (breast feeding) or planning a pregnancy during the course of the study, or who are of child bearing potential and not using a highly effective method of birth control (including sexual abstinence). A highly effective method of birth control is defined as one that results in a low failure rate (i.e. less than 1 percent per year) when used consistently and correctly, such as implants, injectables, combined oral contraceptives, some intrauterine devices (IUDs), sexual abstinence, or a vasectomized partner. Subjects must be willing to continue birth control methods throughout the course of the study.
- 13. History of cancer within the past 3 years (excluding non-melanoma skin cancer and carcinoma in situ of the cervix).
- 14. Life expectancy of less than 2 years.
- 15. Any contraindication or known anaphylactic or severe systemic reaction to either human blood products or materials of animal (bovine, porcine) origin or anesthetic agents.
- 16. Positive for Human Immunodeficiency Virus (HIV), Hepatitis B Virus (HBV), or Hepatitis C Virus (HCV) assessed at the Screening Visit.
- 17. Subjects with active tuberculosis (TB) requiring treatment in the past 3 years.
- 18. Immunocompromised subjects or patients receiving immunosuppressive agents (including patients treated for chronic glomerulonephritis) within 3 months of injection. [Note: inhaled corticosteroids and chronic low-dose corticosteroids [≤ 7.5mg per day] are permitted as are brief pulsed corticosteroids for intermittent symptoms (e.g. asthma).]
- 19. Subjects with uncontrolled diabetes (defined as metabolically unstable by the PI), or with incapacitating cardiac and/or pulmonary disorders.
- 20. History of active alcohol and/or drug abuse that in the investigator's assessment would impair the subject's ability to comply with the protocol.
- 21. Patients with clinically significant hepatic disease (ALT or AST > 3.0 x ULN) at Screening.

- 22. Patients with bleeding disorders that would, in the opinion of the Investigator, interfere with the performance of study procedures; patients taking coumarins (e.g. Warfarin) or other anticoagulants (e.g. enoxaparin or direct thrombin inhibitors).
- 23. Any circumstance in which the investigator deems participation in the study is not in the subject's best interest.
- 24. Use of any investigational product within 3 months of the injection without receiving prior written consent of the Medical Monitor.

Number of Sites: Up to 10 clinical centers will be included in the study.

Study Duration: 18 months NKA injections follow up followed by 24 month long term follow up for a total study duration of 42 months.

Study Enrollment: Up to 30 subjects undergoing NKA injection will be enrolled into the study. Patients who have received a single injection of NKA under previous research protocols may enroll in this clinical trial to receive a single additional injection. Patients who have never received an NKA injection may enroll in this clinical trial for up to a total of two (2) NKA injections, temporally spaced at least 6 months apart. All biopsies are to be taken from a single kidney, and all NKA injections are to be given into the kidney that was biopsied. Patients who complete screening procedures satisfying all I/E criteria will be enrolled into the study immediately prior to the injection. Patients who do not meet all criteria before injection will be considered screen failures. Once a patient has been injected, the patient will have completed treatment and every effort should be made to ensure the patient completes all follow-up visits. Injection dates for the first 3 patients receiving their second NKA injection will be staggered by a minimum of 3 week intervals to allow for assessment of acute adverse events and other safety parameters by the DSMB. Subsequent second injections will continue to be staggered so as to occur no less than 3 weeks apart, but individual DMSB review will not be required. At the completion of the follow-up visits, patients will continue in a long-term follow-up study. Patients will be followed for a total of 36 months following the last NKA injection under this protocol, whether the first or second injection.

Investigational Plan:

Screening: Subjects who satisfy eligibility criteria may be entered into the study. Subjects must have sufficient historical data on renal function to allow for determination of the rate of progression of renal disease prior to injection (Inclusion Criterion 8). Screening procedures will include a full physical examination, electrocardiogram, and laboratory assessments (hematology, serum chemistry, and urinalysis). In addition, an MRI will be performed to assess kidney volume using site standard practices.

Biopsy: Patients not previously enrolled in a Phase 1 trial will require a renal biopsy to obtain the cells for injection. The biopsy specimens obtained from patients previously enrolled in a Phase 1 trial and maintained in a frozen state will be used to generate the second quantum of NKA to be injected under this protocol, if sufficient cells are available after thawing. If the number of cells obtained after thawing the frozen biopsy specimens is insufficient, the patient may need to have an additional biopsy procedure completed for this study.

Injection: Ten to 14 days before the scheduled injection date, subjects will report to the clinic for verification of final eligibility criteria. In addition, a renal scintigraphy study will be performed to obtain a baseline assessment of split kidney function. Subjects who meet appropriate I/E criteria will

be admitted to the hospital/clinical research unit early in the morning on the day of scheduled injection (Day 0). NKA will be injected into the biopsied kidney, using one of two available options: (1) a laparoscopic approach; or (2) a percutaneous approach. The laparoscopic method may utilize robotic assistance to stabilize the kidney while the injection is performed with laparoscopic viewing; while the percutaneous method will employ a standardized technique such as utilized in the ablation of renal masses by radiofrequency or cryogenic methods. Subjects will remain hospitalized for a minimum of 2 nights and up to 4 nights following a laparoscopic injection (or until any procedure- or product-related AE's have resolved or stabilized). Patients may be discharged the same day following a percutaneous injection without complications. An ultrasound study will be performed on Day 1 to verify the lack of subclinical adverse effects for both approaches.

It is anticipated that all patients will be planned to receive 2 injections under this protocol, in order to allow dose-finding and to understand the duration of effect. Under certain circumstances a patient or investigator may decide to postpone or withhold the second dose. In general, if there appears to be any untoward safety risk, in situations including rapid deterioration of renal function, the development of uncontrolled diabetes, or the development of uncontrolled hypertension, or if there is the intercurrent development of a malignancy, the patient should not receive the second dose.

Second injections under this protocol will be staggered so that single injections in different patients occur no less than 3 weeks apart. The DSMB will review the clinical data regarding each of the first 3 second injections under this protocol, and will consult with the Sponsor before the 2nd, 3rd, and 4th second injections are made. Subsequent second injections will continue to be staggered so as to occur no less than 3 weeks apart, but individual DMSB review will not be required.

No staggering will be required for first NKA injections under this protocol.

Post-Injection Follow-up: Subjects will return to the clinic for follow-up safety assessments on Days 7, 14, and 28 post-injection and at 2, 3, and 6 months post-injection. At 6 months post-injection, post-treatment MRI and renal scintigraphy studies will be conducted. After patients complete the 6 month efficacy visit, they will be considered for a second NKA injection. Patients receiving a second dose will follow the same follow up visits that occurred after first injection. Patients 6 month post first injection visit will serve as the patients 14 to 10 day pre- second injection visit. Patients will return for their second injection and at 2, 3, and 6 months post-injection Patients will be followed up to 18 months in the post follow up phase with 6 months after first NKA injection and 12 months after second NKA injection. Refer to the time and events schedule on page 14 for additional post follow up time points.

Long Term Follow-up: Patients will be followed for safety and efficacy for 24 months after the 18 month initial follow up period. Telephone contact will be made 24 and 36 months after the last NKA injection, and visits will be made at 30 and 42 months after the last NKA injection.

NKA Dose: Kidney weight of the target/recipient kidney will be estimated from the results of the MRI taken during Screening. Using the preclinical studies as a guideline, the dose of NKA for this study is 3×10^6 cells/g estimated kidney weight (g KW^{est}). Since the concentration of SRC per mL of NKA is 100 x 10⁶ cells/mL, the dosing volume would be 3 mL for each 100 g or 6 mL for a 200 g kidney. Based on this dosing paradigm, the following doses of NKA would be administered:

Estimated Kidney	Weight (g KW ^{est})	Dose	SRC Delivered						
Median Weight	Weight Range	Volume	(cell number; x						
(g)	(g)	(mL)	106)						
100	95 - 108	3	300						
117	109 - 125	3.5	350						
133	126 - 141	4	400						
150	142 - 158	4.5	450						
167	159 - 175	5	500						
183	176 – 191	5.5	550						
200	192 - 208	6	600						
217	209 - 225	6.5	650						
233	226 - 241	7	700						
250	242 - 258	7.5	750						
	>259	8	800						

Safety Monitoring: While unforeseen adverse effects may occur, the greatest recognized risk to subjects enrolled into the study is hemorrhage following the injection procedure. Therefore, precautions have been taken to minimize the risk of excessive bleeding. Patients with abnormal laboratory values predictive of an increased risk of bleeding will not be eligible for the study. Hemoglobin/hematocrit will be monitored a) before, b) 4 hours after, and c) the day after each procedure.

Injection: During the injection procedure, hemoglobin will be monitored on a regular basis and blood pressure will be monitored continuously using standard site practices. Immediately following laparoscopic injection, the subject will remain supine for 8 hours with regular monitoring of blood pressure/pulse and hemoglobin. The subject will remain in the hospital for 2 to 4 nights following laparoscopic injection for observation of adverse events. On Day 1 following injection, an ultrasound study will be performed to verify there are no subclinical adverse effects. If clinically warranted, an ultrasound may also be performed before discharge from the clinic to ensure no adverse events are ongoing. After an injection via the percutaneous route, the patient may be discharged the same day if that is the site's usual practice after similar procedures (i.e. percutaneous ablation), after no less than 2 hours of observation and monitoring. If product- or procedure-related AE's occurred following surgery, the patient should not be released from the hospital until the AE's have either resolved, stabilized, or returned to baseline. After a laparoscopic injection, the patient should be observed in hospital for 2 to 4 nights to assess for AEs. Following discharge, subjects will be monitored at each visit for changes in renal function including the rate of progression of renal insufficiency. Laboratory values predictive of renal function will be closely monitored. Additional imaging studies may be conducted as needed in response to adverse changes in renal function.

Data Safety Monitoring Board: A Data Safety Monitoring Board (DSMB) will be chartered to oversee patient safety, especially as it relates to any unexpected product-related events. The committee will include 3 members with expertise directly related to protocol activities. The members of the DSMB will have no other engagement with RegenMed (Cayman) Ltd. or any of the study

centers, and the DSMB will function independently. In general, the DSMB will advise RegenMed (Cayman) Ltd. on aspects concerning the safety to the patients who have enrolled as research subjects in the clinical trial. The specific activities and responsibilities of the DSMB will be detailed in the DSMB charter. The DSMB's recommendations will be communicated to the study centers, and where required to the IRBs/ECs, and to the regulatory authorities.

Analysis Methods:

Up to 30 subjects will be injected with NKA. As this is a Phase II safety and early efficacy study, formal sample size calculations were not performed. The planned sample size allows for a preliminary characterization of both the safety profile and potential efficacy of the administered dose of NKA in patients with chronic kidney disease.

Subgroup analyses will compare patients receiving a single injection with patients receiving two injections, and patients receiving laparoscopic injections with patients receiving percutaneous injections.

The safety profile will consist primarily of an evaluation of adverse events, including events of special interest, laboratory parameters, including assessments of renal function, imaging results and vital signs.

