⁶ 24hours post discharge a follow up phone call from the clinic will be conducted to do a wellness check on the subject.

⁷ The informed consent form (ICF) must be signed prior to conducting any study-specific procedures.

⁸ Appropriate selected Inclusion/Exclusion criteria should be reviewed at Screening, and pre-injection.

⁹ Medical and surgical history should be obtained at Screening.

¹⁰ The physical examination (PE) is described in Section 12.2.2.

Confidential

¹¹ Vital signs include heart rate, resting BP, and body temperature. (See section 12.2.3)

- ¹² Vital signs should be measured throughout the procedure.
- ¹³ An ultrasound should be performed 10 to 14 days before injection to verify continued eligibility and on Day 1 following injection to verify lack of adverse events/safety concerns.
- ¹⁴ If clinically indicated due to, for example, bleeding during the procedure or a drop in hemoglobin, an ultrasound may be performed prior to discharge to assess safety concerns.
- ¹⁵ To determine kidney size and volume, an MRI study should be performed between screening and the injection.
- ¹⁶ The patient may be released same day as biopsy per site standard practice, if released same day as biopsy skip day 1 procedures after biopsy.
- ¹⁷ NKA product should be handled and injected according to procedures described in the Study Reference Manual.
- ¹⁸ Record NKA-related SAE's, NKA-related and significant CKD-related AE's reported by the patient at the visit, and ongoing CKD-specific medications.
- ¹⁹ KDQOL Survey will be completed at pre-injection and at day 28 and months 3, 6, 9, 12, 15, 18, 30 and 42 months after second NKA injection.

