4 TIME AND EVENTS SCHEDULE: LABORATORY ASSESSMENTS

Event	Scr ¹	Bi	opsy	y ²		Pre-		Inject	tion $(1)^{3}$	Fo	ollow	-up	1 st Inj Follo	ection w-up	Pre-2 nd Injectio	2	nd Injec (Hosp.	tion .) ³	2 nd Fo	Injeo ollow	ction /-up		F	Follow (± 7 d	-up ay)		Long	Term (± 7	Follo [,] day)	w Up
						mpi.	 	(1105)	J.)	(-	- 5 u	iy)	(± 7	day)	n		r		(=	± 3 d:	ay)						24	20	26	12
Laboratory Assessment	≤45d pre- biopsy	3 to 1 day	Biopsy	1 day		14 to 10 days	D0	Inpt ⁴	Disch ⁵	D7	D14	D28	2 mo	3mo	6mo (14 to 10 day)	D0	Inpt ^{.4}	Disch ⁵	D7	D14	D28	8mo	9mo	12mo	15mo	18mo EOS ⁶	24mo Call	30mo Visit	Call	42mo Visit
Chemistry ⁷					J.																									
 Std. panel 	Х	Х		Х	io e	Х	Х	Х	Х	Х	Х	Х	Х	Х	Х	Х	Х	Х	Х	Х	Х	Х	Х	Х	Х	Х		Х		Х
• Renal	Х	Х		Х	ture	Х	Х	Х	Х	Х	Х	Х	Х	Х	Х	Х	Х	Х	Х	Х	Х	Х	Х	Х	Х	Х		Х		Х
 Pregnancy test⁸ 	Х	Х			fac	Х			l						Х															
• HIV, HBV, HCV	Х	Х			nun				l																					
 Lipid Panel 	Х				ma	Х									Х															
Hematology ⁹	Х	Х		Х	pu	Х		Х	X	Х	Χ	Х	Х	Х	Х		Х	Х	Х	Х	Х	Х	Х	Х	Х	Х				
• Multiple ¹⁰			Χ		n a		Х									Х														
Coag. Status	X	Χ			ctio	X									Х															
Urinalysis					cA																									
• 24 hour	X				II se									X									Χ	Х	Х	Χ				
 Spot urine 	Х	Х			cel	Х				Х		Х	Х	Х	Х				Х		Х	Х	Х	Х	Х	Х		Х		X
 Test stick 				Х	nal	Х	X ¹¹								Х	X^{11}														
Add. Tests:					Re																									
• HbA1c	X				S:																			X		Х		Х		X
Beta 2microblobulin ¹²	Х	Х			week	Х						Х			Х						Х			Х		Х				
• iPTH	Х	Х			14	Х			l			Х		Х	Х						Х			Х		Х				
• Research (reserve) Samples ¹³	Х	х			4	Х						Х	Х	Х	Х						Х	Х	X	Х	Х	Х		Х		Х

¹ Screening assessments should be conducted within the 45 days prior to the injection; if assessments fall outside of the 45 day window, rescreening should be conducted as discussed in Section 11.1.

² Patient may be released same day as biopsy per site standard practice, if released same day as biopsy skip day 1 procedures after biopsy. Note that returning patients may not need a biopsy to be completed and will go from screening to the pre-injection visit.

³ Patients receiving percutaneous approach will have Day 0 lab assessments and then skip to day 7 assessments.

⁴ Inpatient Hospital days, Days 1 and possibly Days 2 and 3 depending on day of discharge.

⁵ The patient will be discharged as early as Day 2 and as late as Day 4 following laparoscopic injection, or Day 1 following percutaneous injection. Refer to Section 11.4 for discharge instructions.

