11.3 Injection (Study Days -14 to 4)

Due to shipping and manufacturing schedules, NKA injection should be scheduled for Wednesday, Thursday, or Friday. If it is necessary to schedule the injection for Tuesday, the site should contact RegenMed (Cayman) Ltd. before scheduling the injection to make sure Tuesday injection can be accommodated. NKA injection should not be scheduled on a Monday.

Patients should report to the clinic ten to 14 days before the scheduled injection (Day -10 to -14) for pre-injection assessments to verify the continued eligibility of the patient. If the patient is still eligible following review of the results of the assessments, the site will conduct the baseline renal scintigraphy study and contact RegenMed (Cayman) Ltd. indicating that NKA product should be produced. If the patient is not eligible for injection, the site should contact RegenMed (Cayman) Ltd. to alert manufacturing staff not to thaw the patient's frozen renal cells and manufacture NKA. The PI should contact RegenMed (Cayman) Ltd. to discuss the reason(s) the patient did not qualify and determine the best course of action. For example, if the patient was excluded for a temporary condition (e.g., active infection) then it may be possible to manufacture NKA at a later date such that the patient could be injected when he/she became eligible. If the patient's results indicate that it is highly unlikely that the patient would become eligible within an acceptable time frame, then the patient should be discontinued from the study. [Note that in the latter case, the patient can be replaced.] If injection is delayed, the renal scintigraphy study, if conducted, does not need to be repeated prior to injection.

For injection, patients should arrive at the clinic the day of the scheduled injection day (Day 0). The patient should be injected according to procedures discussed below (Section 8.2.2). On Day 1 post-injection, an ultrasound should be performed to verify lack of subclinical adverse effects (e.g., swelling, fluid accumulation). If clinically warranted, an additional ultrasound may be performed prior to discharge to verify lack of subclinical events.

```
Confidential
```

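### After percutaneous injection, the visit and laboratory schedules do not deliver the Day 1 hemoglobin and Day 1 ultrasound that the protocol text requires

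*Combined protocol and SAP*

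**What the plan says.** **Hemoglobin.** The Safety Monitoring paragraph of the synopsis sets the timing for every procedure and every route: "Hemoglobin/hematocrit will be monitored a) before, b) 4 hours after, and c) the day after each procedure". Footnote 3 of the laboratory schedule (Section 4) reads: "Patients receiving percutaneous approach will have Day 0 lab assessments and then skip to day 7 assessments".

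**Ultrasound.** The Injection paragraph of the synopsis, directly after allowing same-day discharge for the percutaneous route, says: "An ultrasound study will be performed on Day 1 to verify the lack of subclinical adverse effects for both approaches". The Safety Monitoring text repeats it ("On Day 1 following injection, an ultrasound study will be performed to verify there are no subclinical adverse effects"), and so does Section 11.3 ("On Day 1 post-injection, an ultrasound should be performed to verify lack of subclinical adverse effects"). Footnote 13 under each percutaneous Time and Events Schedule asks for a scan "on Day 1 following injection to verify lack of adverse events/safety concerns".

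**Biopsy.** Footnote 2 of the laboratory schedule says of the biopsy patient: "if released same day as biopsy skip day 1 procedures after biopsy". Footnote 16 of the visit grids has the same rule.

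**Which document the sites follow.** Section 11 directs that subjects be followed according to the visit schedule and the laboratory schedule. I found no rule saying whether text or schedule prevails when they differ.

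**The concern.** The synopsis treats hemorrhage after injection as the leading recognized hazard, and the Day 1 hemoglobin and Day 1 scan are the checks placed there to find it, including bleeding without symptoms. A site that follows laboratory footnote 3 as written omits the first check. A site that works from the grid cells omits the second.

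The gap falls on the newer route. Section 6.6.2 says the percutaneous approach is introduced in this version of the protocol. Section 6.5.2 credits laparoscopy with a direct view of the kidney, so that bleeding can be seen and dealt with at once. The route without that view has the thinner Day 1 schedule. This is a matter of patient safety and of consistent conduct across up to 10 sites. It affects no sample size or error rate.

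**Working it through.** The plan states no figure to reproduce. The check sets text against schedule and counts columns in the grids.

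1. **Day 1 hemoglobin, percutaneous.** Required: before, at 4 hours and on the next day (synopsis). Scheduled: Day 0, then Day 7 (laboratory footnote 3). Footnote 10 of the laboratory schedule asks for local hemoglobin and hematocrit on procedure days only, so it does not supply the next-day draw. Section 11.4 allows 3 days around Day 7: 7 − 3 = Day 4 and 7 + 3 = Day 10. The next scheduled value is therefore between Day 4 and Day 10.

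2. **Day 1 ultrasound, percutaneous.** The D1 column can be fixed from the Telephone Call row, whose footnote-6 mark falls there. Reading the Ultrasound/CT row from the injection day on:
   - Second-dose-only grid: D0 marked with footnote 14 (a discretionary scan before discharge), D1 blank, next mark at 6 months.
   - New-patient grid: first D0 marked with footnote 14, D1 blank, 6 months marked, second D0 marked with footnote 14, D1 blank.

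   In both grids D1 carries the call, adverse events and concomitant medications. Vital signs are blank, so no attendance is built in. In the laparoscopic grids, by contrast, the ultrasound row is ticked in the inpatient column, which covers Day 1.

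3. **Count.** Day 1 hemoglobin/hematocrit (1) + Day 1 ultrasound (1) = 2 checks per percutaneous injection. For a patient given two percutaneous injections under this protocol, 2 × 2 = 4.

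4. **Biopsy (secondary).** The synopsis rule covers each procedure, and hematology is ticked one day after biopsy. Laboratory footnote 2 and grid footnote 16 remove it for patients sent home the same day. Section 11.2 places biopsy 4 to 14 weeks (28 to 98 days) before injection, and the pre-injection visit is 14 to 10 days before injection. The next scheduled hematology is thus 28 − 14 = 14 days to 98 − 10 = 88 days after biopsy. Section 12.5.1 does provide hemoglobin monitoring during the 4 hours the patient lies supine.

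**The case against.** **The scan is not waived.** A reader might infer from the blank cells that percutaneous patients are exempt from the Day 1 ultrasound. The documents do not support that. Footnote 13 under the same grids still orders it, and the synopsis applies it to both routes. What is missing is a tick and a visit. This part of the objection stands, and it makes the ultrasound item a failure of scheduling, not a contradiction of rules. It does not remove the problem, because an instruction with only a telephone call attached cannot be carried out as scheduled.

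**Footnote 3 may govern only central-laboratory samples.** Section 12.3 sends scheduled samples to a central laboratory, and footnote 10 separates local values used for clinical care. On that reading the synopsis rule would survive alongside footnote 3. Nothing in the protocol states this limit. Section 13.4.1 asks for regular hemoglobin monitoring after both procedures but gives no times.

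**Other safeguards exist.** Section 12.5.2 provides CT or color Doppler at completion, 2 to 3 hours of observation, discharge only when indices are normal, and a call 24 hours after discharge. Patients with related adverse events are kept in hospital. These lower the risk, but none of them measures hemoglobin or images the kidney on Day 1.

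**Three further inferences should not be drawn.**
- Discharge timing may look contradictory, because laboratory footnote 5 says "or Day 1 following percutaneous injection" and the grids allow the same day. Section 9 allows 0 to 1 night, which covers both.
- Discharge from 2 hours may seem to contradict the 4-hour hemoglobin. Two hours is a minimum, and a site that waits satisfies every rule.
- Unequal checking may seem to call for a caveat on the comparison by route in Section 14.8. Sections 14.7.2 to 14.7.4 already plan no inferential statistics for adverse events or for laboratory data other than progression rate, and only listings and descriptive statistics for ultrasound.

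**The sponsor could waive the checks instead.** That is a clinical choice open to it, but the synopsis, Section 11.3 and footnote 13 would then have to say so. At present they say the reverse.

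**Conclusion.** The point holds and should be fixed. The hemoglobin item is a direct conflict between the synopsis and laboratory footnote 3. The ultrasound item is a requirement stated in the synopsis, Section 11.3 and footnote 13 for which the percutaneous schedules give no tick and no visit. The size is two checks per percutaneous injection, four for a patient treated twice by that route, with the next scheduled hemoglobin at Day 7 (Day 4 to Day 10). The biopsy conflict is secondary: an explicit skip rule set against a synopsis sentence that covers every procedure.

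This assumes that sites follow the schedules, as Section 11 directs, and that the unqualified synopsis wording means what it says. The documents give no basis for estimating how many bleeds would be missed or found late.

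**What to change.** - Amend laboratory footnote 3 so that percutaneous patients have hemoglobin/hematocrit on Day 1 before moving to Day 7.
- In both percutaneous grids, add a Day 1 ultrasound tick and a Day 1 clinic visit after each injection. An overnight stay would also serve, within the 0 to 1 night that Section 9 allows.
- Amend laboratory footnote 2 and grid footnote 16 so that patients discharged on the day of biopsy still have a Day 1 hemoglobin/hematocrit.

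Beyond the wording changes, the cost for same-day-discharge patients is one Day 1 return or one night per percutaneous injection, and one blood draw after biopsy. The synopsis already requires these checks, so the amendment adds no new obligation. No change to Section 14.8 or to the discharge rules is needed for this point.
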